The target enrollment is up to 500 participants (minimum of 300) for each study arm (1:1). The assumptions are: 1) at least CCI participants will be in the 4th dose subgroup; and 2) CCI of participants will be excluded from the PP set for immunogenicity, SARS-CoV-2 negative (eg, due to infection with the SARS-CoV-2 Omicron variant).

Day 29:

With approximately CCI evaluable participants per arm, there is CCI power to demonstrate non-inferiority of mRNA-1273.529 against the B.1.1.529 strain at 2-sided alpha of 1.0% at Day 29. With this range of sample sizes, the power to demonstrate superiority of mRNA-1273.529 against the B.1.1.529 variant strain at a 2-sided alpha of 1% at Day 29 ranges from CCI. The assumptions are: the true GMT ratio (mRNA-1273.529 vs mRNA-1273) ranges from CCI, the standard deviation of the natural log-transformed titer is CCI, with a non-inferiority margin of 1.5.

Month 3:

With approximately CCI [REDACTED] evaluable participants per arm, there is CCI [REDACTED] power to demonstrate non-inferiority of mRNA-1273.529 against the B.1.1.529 strain at 2-sided alpha of 4.0% at Month 3. With this range of sample sizes, the power to demonstrate superiority of mRNA-1273.529 against the B.1.1.529 variant strain at a 2-sided alpha of 4% at Month 3 ranges from CCI [REDACTED]. The assumptions are: the true GMT ratio (mRNA-1273.529 vs mRNA-1273) ranges from CCI [REDACTED], the standard deviation of the natural log-transformed titer is CCI [REDACTED], with a non-inferiority margin of 1.5. Specific operating characteristics are presented in the table below.

With approximately CCI [REDACTED] participants receiving the 4th dose in each study arm, there is at least 90% probability to observe one participant reporting an AE in each study arm if the true incidence of AEs is 1%.

Operating Characteristics for Part 1:

True GMR (mRNA-1273.529 vs. mRNA-1273 against B.1.1.529)	Number evaluable patients per arm (4 th dose)	Minimum empirical GMR for the primary objective	Power
Two-sided Type I Error (α) = 0.01 (Day 29)			
Primary Objective: Non-inferiority (lower bound of the $(1-\alpha) * 100\%$ of GMR ≥ 0.67)			
			
Key Secondary Objective: Superiority (lower bound of the $(1-\alpha) * 100\%$ of GMR rules out 1)			
			
Two-sided Type I Error (α) = 0.04 (Month 3)			

Primary Objective: Non-inferiority (lower bound of the $(1-\alpha) * 100\%$ of GMR ≥ 0.67)
 
CCI


Key Secondary Objective: Superiority (lower bound of the $(1-\alpha) * 100\%$ of GMR rules out 1)
 
CCI

Abbreviations: GMR = geometric mean titer ratio; mRNA = messenger ribonucleic acid.

Part 2 (50 µg mRNA-1273.214 and 50 µg mRNA-1273 in 1:1 randomization)

The primary immunogenicity objective in Part 2 of this study is to assess immune response of mRNA-1273.214 against the B.1.1.529 and prototype strains in participants receiving mRNA-1273.214 (or mRNA-1273) as the 4th dose. The sample size is driven by this subgroup.

Hypotheses testing on immunogenicity data will be performed at 2 timepoints of interest (Day 29 and Month 3 post-booster). To preserve family-wise alpha of 0.05 (2-sided), alpha will be allocated to Day 29 of 0.01 (2-sided) and Month 3 of 0.04 (2-sided).

Statistical power for hypotheses testing at Day 29 (alpha=0.01, 2-sided):

For the 4th dose subgroup, the target enrollment is approximately 1328 participants for each treatment arm (1:1). Assuming CCI of participants will be excluded from the PP Set for Immunogenicity, SARS-CoV-2 negative, with approximately CCI evaluable participants in each arm, there is CCI power to demonstrate non-inferiority of mRNA-1273.214 against the B.1.1.529 and prototype strains at 2-sided alpha of 1.0%. With this sample size, there is approximately CCI power to demonstrate superiority of mRNA-1273.214 against the B.1.1.529 variant strain at a 2-sided alpha of 1.0% at Day 29. The assumptions are: the true GMT ratio (mRNA-1273.214 vs. mRNA-1273) against the B.1.1.529 strain ranges from CCI and the true GMT ratio (mRNA-1273.214 vs. mRNA-1273) against the

prototype is █, the standard deviation of the natural log-transformed titer is █, with a non-inferiority margin of 1.5.

Statistical power for hypotheses testing at Month 3 (alpha=0.04, 2-sided):

With approximately █ evaluable participants in each arm, there is █ power to demonstrate non-inferiority of mRNA-1273.214 against the B.1.1.529 strain and against prototype strain at 2-sided alpha of 4.0% at Month 3. With this sample size, there is approximately █ power to demonstrate superiority of mRNA-1273.214 against the B.1.1.529 variant strain at a 2-sided alpha of 4.0% at Month 3. The assumptions are: the true GMT ratio (mRNA-1273.214 vs. mRNA-1273) against the B.1.1.529 strain ranges from █ █ and the true GMT ratio (mRNA-1273.214 vs. mRNA-1273) against the prototype is █, the standard deviation of the natural log-transformed titer is █, with a non-inferiority margin of 1.5.

With approximately 1328 participants receiving the 4th dose in each study arm, there is at least 90% probability to observe one participant reporting an AE in each study arm if the true rate incidence of AEs is 1%.

The enrollment target of this study is approximately 1328 participants per arm to receive the 4th dose. The Omicron VOC has spread quickly throughout the world as the predominant circulating SARS-CoV-2 strain globally. There may be an urgency to perform Day 29 or Month 3 analysis as early as possible. Depending on the operational feasibility, particularly the testing capability of assays of antibodies against B.1.1.529, the Sponsor may decide to perform the analysis of immunogenicity after immunogenicity data from a subset of the participants receiving the 4th dose becomes available. Such a decision will be documented prior to the planned analysis at Day 29 or Month 3.

The power and operating characteristics for Part 2 under various GMT ratios and 2 different scenarios for the number of evaluable participants with immunogenicity data are provided in the table below. Based on █ evaluable participants per arm (4th dose), under the same assumptions outlined above, there is █ power to demonstrate non-inferiority of mRNA-1273.214 compared to mRNA-1273 against the B.1.1.529 at Day 29 at $\alpha = 1\%$ if true GMT ratio █; and there is approximately █ power to demonstrate superiority at $\alpha = 1\%$ if the true ratio is █. With this size, there is █ power at Month 3 (primary objective) at $\alpha = 4\%$ (2-sided) if the true GMT ratio is █; and there is █ power to demonstrate superiority at $\alpha = 4\%$ (2-sided) if the true GMR is █.

Operating Characteristics for Part 2:

True GMR (mRNA-1273.214 vs. mRNA-1273 against B.1.1.529)	Number evaluable patients per arm (4 th dose)	Minimum empirical GMR for the primary objective	Power
--	--	--	-------

Two-sided Type I Error (α) = 0.01 (Day 29)

Primary Objective: Non-inferiority (lower bound of the $(1-\alpha) * 100\%$ of GMR ≥ 0.67)

CCI

Primary Objective: Superiority (lower bound of the $(1-\alpha) * 100\%$ of GMR rules out 1)

CCI

Two-sided Type I Error (α) = 0.04 (Month 3)

Primary Objective: Non-inferiority (lower bound of the $(1-\alpha) * 100\%$ of GMR ≥ 0.67)

CCI

Primary Objective: Superiority (lower bound of the $(1-\alpha) * 100\%$ of GMR rules out 1)

CCI

Abbreviations: GMR = geometric mean titer ratio; mRNA = messenger ribonucleic acid.

Analysis Populations (Part 1 and Part 2):

Set	Description
Full Analysis Set (FAS)	The FAS consists of all randomized participants who receive the IP. Participants will be analyzed according to their randomized study arm.
Modified Intent-to-Treat (mITT) Set	The mITT Set consists of all participants in the FAS who have no serologic or virologic evidence of prior SARS-CoV-2 infection (both negative RT-PCR test for SARS-CoV-2 and negative serology test based on bAb specific to SARS-CoV-2 nucleocapsid) prebooster, ie, all FAS participants with pre-booster/baseline SARS-CoV-2 negative status. Participants will be analyzed according to their randomized study arm.
PP Set for Immunogenicity (PPSI)	The PPSI consists of all participants in the FAS who receive the planned dose of study vaccination and have no major protocol deviations that impact key or critical data. Participants will be analyzed according to their randomized study arm.
PP Set for Immunogenicity – SARS-CoV-2 negative (PPSI-Neg)	Participants in the PPSI who have no serologic or virologic evidence of SARS-CoV-2 infection up to day of visit analysis, ie, who are SARS-CoV-2 negative, defined by both negative RT-PCR test for SARS-CoV-2 and negative serology test based on bAb specific to SARS-CoV-2 nucleocapsid. PPSI-Neg will be the primary analysis set for analyses of immunogenicity unless otherwise specified.
Solicited Safety Set	The Solicited Safety Set consists of all randomized participants who receive IP and contribute any solicited AR data. The Solicited Safety Set will be used for the analyses of solicited ARs. Participants will be included in the study arm that they actually received.
Safety Set	The Safety Set consists of all randomized participants who receive IP. The Safety Set will be used for all analyses of safety except for the solicited ARs. Participants will be included in the study arm that they actually received.
PP Set for Efficacy (PPSE)	The PPSE consists of all participants in the mITT who receive the planned study vaccination and have no major protocol deviations that impact key or critical data.

Abbreviations: AR = adverse reaction; FAS = full analysis set; IP = investigational product; mITT = modified intent-to-treat; PP = Per protocol; RT-PCR = reverse transcription polymerase chain reaction; SARS-CoV-2 = severe acute respiratory syndrome coronavirus 2.

Immunogenicity Analysis:

Part 1: mRNA-1273.529 vs. mRNA-1273

The primary objective on immune response in Part 1 of this study is based on the participants who will receive the 4th dose in the study. There is 1 hypothesis on immune response of mRNA-1273.529. Part 1 is considered to meet its primary objective if non-inferiority of mRNA-1273.529 against the B.1.1.529 strain is demonstrated as compared to mRNA-1273 (primary hypothesis).

An analysis of covariance (ANCOVA) model will be performed to assess the difference in immune response between mRNA-1273.529 and mRNA-1273 as the 4th dose in the subgroup of participants who received the 4th dose. This analysis will be carried out for immune response against the B.1.1.529 strain and the prototype virus strain separately in the PPSI-Neg analysis population.

Specifically, for immune response against the B.1.1.529 strain, in the ANCOVA model, antibody titers at Day 29 post-booster against the B.1.1.529 strain will be a dependent variable, and a group variable (mRNA-1273.529 and mRNA-1273) will be the fixed effect, adjusting for age groups (< 65, ≥ 65 years) and pre-booster antibody titer level, if applicable. The GMT will be estimated by the geometric least square mean (GLSM) from the model and its corresponding 99% CIs will be provided for each group. The GMR (ratio of GMTs) for mRNA-1273.529 with respect to mRNA-1273 will be estimated by the ratio of GLSM from the model and the corresponding 99% CIs will be provided. The 99% CI for GMR will be used to assess the between group difference in immune response against the B.1.1.529 strain for mRNA-1273.529 at Day 29 compared to the mRNA-1273 as a booster for non-inferiority testing.

Against the B.1.1.529 strain, the non-inferiority of immune response of mRNA-1273.529 as compared to mRNA-1273 will be considered demonstrated if the lower bound of the corresponding 99% CI is ≥ 0.67 (Day 29) based on a non-inferiority margin of 1.5.

Once non-inferiority against B.1.1.529 is demonstrated, superiority of mRNA-1273.529 as compared to mRNA-1273 against B.1.1.529 will be tested; if the lower bound of the 99% CI of the GMT ratio is > 1 (Day 29), superiority is demonstrated.

The same ANCOVA model will be used to assess immune response of mRNA-1273.529 against the B.1.1.529 strain at Month 3; 96% CI for GMR will be used to assess the between group difference in immune response against the B.1.1.529 strain for non-inferiority and superiority. For the immune response against the prototype virus strain, the same analysis method will be used.

Part 2: mRNA-1273.214 vs. mRNA-1273

The primary objective on immune response in Part 2 of this study is based on the participants who will receive the 4th dose in Part 2 of the study. There are 6 hypotheses on the immune response of mRNA-1273.214 (see figure above). Part 2 is considered to meet its primary objective if non-inferiority of mRNA-1273.214 against the B.1.1.529 strain, non-inferiority of mRNA-1273.214 against the prototype, and superiority of mRNA-1273.214 against the B.1.1.529 strain are demonstrated as compared to mRNA-1273 at any of the following time points post-booster: Day 29, Month 3.

An ANCOVA model will be carried out to assess the difference in immune response between mRNA-1273.214 and mRNA-1273 in the subgroup of participants who received the 4th dose. This analysis will be carried out for the immune response against the B.1.1.529 strain and the prototype virus strain separately using the PPSI-Neg analysis population.

Specifically, for immune response against the B.1.1.529 strain, in the ANCOVA model, antibody titers at Day 29 post-booster against the B.1.1.529 strain will be a dependent variable, and a group variable (mRNA-1273.214 and mRNA-1273) will be the fixed effect, adjusting for age groups (< 65, ≥ 65 years) and pre-booster antibody titer level, if applicable. The GMT will be estimated by the geometric least square mean (GLSM) from the model and its corresponding 99% CIs will be provided for each group. The GMR (ratio of GMTs) for mRNA-1273.214 with respect to mRNA-1273 will be estimated by the ratio of GLSM from the model and the corresponding 99% CIs will be provided. The 99% CI for GMR will be used to assess the between group difference in immune response against the B.1.1.529 strain for mRNA-1273.529 at Day 29 compared to the mRNA-1273 as a booster for non-inferiority testing.

Against the B.1.1.529 strain, the non-inferiority of immune response of mRNA-1273.214 as compared to mRNA-1273 will be considered demonstrated if the lower bound of the corresponding 99% CI is ≥ 0.67 based on a non-inferiority margin of 1.5.

Once non-inferiority against B.1.1.529 is demonstrated, superiority of mRNA-1273.214 as compared to mRNA-1273 against B.1.1.529 will be tested (at Day 29); if the lower bound of the 99% CI of the GMR ratio is > 1, superiority is demonstrated.

The same ANCOVA model will be used to assess immune response of mRNA-1273.214 against the B.1.1.529 strain at Month 3; 96% CI for GMR will be used to assess the between group difference in immune response against the B.1.1.529 strain for non-inferiority and superiority. For the immune response against the prototype virus strain, the same analysis method will be used.

As part of the secondary analysis to assess for immune response against other variants, the same analysis method described above will be used. A 95% CI for GMR will be used to assess for non-inferiority and superiority.

The following section is applicable to both Part 1 and Part 2:

Immunogenicity, SARS-CoV-2-specific bAb and nAb, will be assessed at multiple timepoints in this study. Mixed effects models will be used to analyze all post-booster/baseline measures. The models will include treatment group, analysis visit, treatment by visit interaction, and adjustment for age groups and pre-booster titer levels. An unstructured covariance structure will be used to model the within-participant errors. The GMT will be estimated from the model and its corresponding 95% CI will be provided for each group at each post-boost timepoint. The GMR (ratio of GMTs) for mRNA-1273.529 and for mRNA-1273.214 with respect to mRNA-1273 will be estimated from each model and the corresponding 95% CI will be provided at each post-boost time point.

For each of the antibodies of interest (eg, levels of SARS-CoV-2-specific bAb and SARSCoV-2-specific nAb), the GMT or level with corresponding 95% CI at each time point, and GMFR of post-booster/pre-booster titers or levels with corresponding 95% CI at each post baseline time point will be provided for each arm. The 95% CIs will be calculated based on the t-distribution of the log-transformed values then back-transformed to the original scale for presentation. The following descriptive statistics will also be provided at each time point: number of participants (n), median, minimum, and maximum. PPSI will be used as the analysis population to summarize the immune responses (antibodies of interest) and the above summary statistics including GMT and GMFR will be provided by pre-booster/study baseline SARS-CoV-2 status.

SRR definitions and analyses will be defined in the SAP.

Planned Analyses

The planned analyses of immunogenicity and safety will be conducted after participants have completed Day 29 and Month 3 visit assessments. Analyses of the Month 6 and Month 12 visit including the Phase B (open-label, observational) part of the study will be exploratory.

The final analysis of all endpoints will be performed after all participants have completed or discontinued from the study. Results of this analysis will be presented in a final CSR.

Efficacy Analyses:

Number and incidence rates of symptomatic COVID-19 disease, asymptomatic SARS-CoV-2 infection, as well as COVID-19 regardless of symptoms will be provided for each study arm. Vaccine efficacy may be estimated if the number of cases accrued is deemed to be sufficient.

Efficacy analyses will be performed using the mITT and PP Set for Efficacy analysis populations. The details will be provided in SAP.

Safety Analyses:

All safety analyses will be based on the Safety Set, except analyses of solicited ARs, which will be based on the Solicited Safety Set.

Safety and reactogenicity will be assessed by clinical review of all relevant parameters including solicited ARs (local and systemic ARs), unsolicited AEs, and physical examination findings.

The number and percentage of participants with any solicited local AR, with any solicited systemic AR, with any solicited AR during the 7-day follow-up period after vaccination, and with Grade 3 or higher solicited AR will be provided. A 2-sided 95% exact CI using the Clopper Pearson method will be provided for the percentage of participants with any solicited AR.

[figure not shown]
The number and percentage of participants with unsolicited AEs, treatment-related AEs, severe AEs, SAEs, MAAEs, AESIs, and AEs leading to withdrawal will be summarized. Unsolicited AEs will be presented by MedDRA system organ class and preferred term. Unsolicited AEs will be coded according to the MedDRA Dictionary for Adverse Reaction Terminology.

Pregnancy outcomes will also be summarized.

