1. PROTOCOL SUMMARY

1.1. Protocol Synopsis

Name of Sponsor/Company: ModernaTX, Inc.	
Name of Investigational Products: mRNA-1273.529, mRNA-1273.214	
Protocol Title: A Phase 2/3, Randomized, Observer-blind, Active-controlled, Multicenter Study to Evaluate the Immunogenicity and Safety of Omicron Variant Vaccines in Comparison with mRNA-1273 (Prototype) Booster Vaccine	
Protocol Number: mRNA-1273-P305, Amendment 2	
Study Duration: Approximately 13 months	
Phase of Development: Phase 2/3	
Estimated Date First Participant Enrolled: 07 Feb 2022	
Estimated Date Last Participant Completed: 07 Apr 2023	
Site Locations: Multicenter study in the UK	
Objectives and Endpoints	
Part 1: mRNA-1273.529 and mRNA-1273	
Objectives	Endpoints
Primary	
To demonstrate non-inferiority of the immune response of mRNA-1273.529 compared to mRNA-1273 booster administered as a 4 th dose against the B.1.1.529 strain at Day 29 or Month 3	
Geometric mean titer (GMT) of mRNA-1273.529 and mRNA-1273 against the B.1.1.529 strain at Day 29 and Month 3 after study vaccine administrationRatio of $GMT_{mRNA-1273.529}/GMT_{mRNA-1273}$ against the B.1.1.529 strain at Day 29 and Month 3 after study vaccine administration
To evaluate the safety and reactogenicity of mRNA-1273.529 and	
Solicited local and systemic reactogenicity ARs during a 7-day follow up period after vaccination

mRNA-1273 administered as a booster dose	
 Unsolicited AEs during the 28-day follow-up period after vaccination SAEs, medically attended AEs (MAAEs), AEs leading to withdrawal, and AEs of special interest (AESIs) from Day 1 to end of study
Secondary	
Key Secondary	
To demonstrate superiority of the immune response of mRNA-1273.529 compared to mRNA-1273 administered as a 4 th dose against the B.1.1.529 strain at Day 29 or Month 3	
 GMT of mRNA-1273.529 and mRNA-1273 against the B.1.1.529 strain at Day 29 and Month 3 after study vaccine administration Ratio of $GMT_{mRNA-1273.529}/GMT_{mRNA-1273}$ against the B.1.1.529 strain at Day 29 and Month 3 after study vaccine administration
Other Secondary	

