9.6.3. Safety Analyses

All safety analyses will be based on the Safety Set, except analyses of solicited ARs, which will be based on the Solicited Safety Set.

Safety and reactogenicity will be assessed by clinical review of all relevant parameters including solicited ARs (local and systemic ARs), unsolicited AEs, and physical examination findings.

The number and percentage of participants with any solicited local AR, with any solicited systemic AR, with any solicited AR during the 7-day follow-up period after vaccination, and with Grade 3 or higher solicited AR will be provided. A 2-sided 95% exact CI using the Clopper Pearson method will be provided for the percentage of participants with any solicited AR.

The number and percentage of participants with unsolicited AEs, treatment-related AEs, severe AEs, SAEs, MAAEs, AESIs, and AEs leading to withdrawal will be summarized. The follow-up windows for AEs are detailed in the SoE ([Table 1](#) and [Table 2](#)). Unsolicited AEs will be presented

by MedDRA system organ class and preferred term. Unsolicited AEs will be coded according to the MedDRA Dictionary for Adverse Reaction Terminology.

Pregnancy outcomes will also be summarized.

[Table 12](#) summarizes the analysis strategy for safety parameters. Further details will be described in the SAP.

Table 12: Analysis Strategy for Safety Parameters

Safety Endpoint	Number and Percentage of Participants, Number of Events	95% CI
Any solicited AR (overall and by local, systemic)	X	X
Any unsolicited AE	X	—
Any SAE	X	—
Any AESI	X	—
Any unsolicited MAAE	X	—
Any unsolicited treatment-related AE	X	—
Any treatment-related SAE	X	—
Discontinuation due to AE	X	—
Any severe AE	X	—
Any treatment-related severe AE	X	—

Abbreviations: AE = adverse event; AESI = adverse event of special interest; AR = adverse reaction; CI = confidence interval; MAAE = medically attended adverse event; PT = preferred term; SAE = serious adverse event; SOC = system organ class.

Notes: 95% CI using the Clopper-Pearson method, X = results will be provided. Unsolicited AEs will be summarized by SOC and PT coded by MedDRA.

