2.1.2. Primary Safety Objective

Part 1

- To evaluate the safety and reactogenicity of mRNA-1273.529 and mRNA-1273 administered as a booster dose.

Part 2

- To evaluate the safety and reactogenicity of mRNA-1273.214 and mRNA-1273 administered as a booster dose.

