6.3.1. Adverse Events

A treatment-emergent AE (TEAE) is defined as any event occurring during the study that was not present before exposure to study vaccine, or any event already present that worsens after exposure to study vaccine. Worsening of a pre-existing condition after vaccination will be reported as a new AE.

Adverse events will also be evaluated by the investigator for the coexistence of MAAE which is defined as an AE that leads to an unscheduled visit to a healthcare practitioner.

Refer to Protocol Appendix 3 for the definitions of AEs of special interest (AESI).

Analyses of unsolicited AEs will be summarized by stage, up to 28 days after vaccination and throughout the study and by treatment group ([Section 6.1](#)).

All summary tables (except for the overall summary of AEs) for unsolicited AEs will be presented by SOC and PT for TEAEs with counts of participants included. When summarizing the number and percentage of participants with an event, participants with multiple occurrences of the same AE or a continuing AE will be counted once. Participants will be presented according to the highest severity (the strongest causality) in the summaries by severity (of related AEs), if participants reported multiple events under the same SOC and/or PT.

Percentages will be based upon the number of participants in the Safety Set.

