6.3.2. Solicited Adverse Reactions

The SARs are recorded by the participant in eDiary on the day of injection and for the 6 days post injection. If a solicited local or systemic AR starts more than 7 days after dosing, it should be captured on the AE page until resolution, not to exceed 28 days after vaccination. If a solicited local or systemic AR continues beyond 7 days post injection, the participant should notify the site to provide an end date and close out the event. ARs beyond Day 7 should be reviewed by the clinic staff either during the next scheduled telephone call or at the next clinic visit, or during an unscheduled visit.

Analyses of SARs within 7 Days will be provided based on the Solicited Safety Set. Analyses of SARs with Onset after Day 7 will be provided based on the Safety Set. The following summaries will be provided

- Summary of SAR Within 7 Days (SAR eDiary and SAR eCRF)
 - i. The number and percentage of participants who reported individual solicited local AR and/or solicited systemic AR during the 7-day follow-up period after the injection will be tabulated by severity grade, and by severity grade and day of reporting.

A two-sided 95% exact confidence interval (CI) using the Clopper-Pearson method will be provided for the percentage of participants who reported any solicited local AR, solicited systemic AR, or any SAR.

- ii. The number and percentage of participants who reported individual solicited local AR and/or solicited systemic AR during the 7-day follow-up period after the injection will be summarized by onset day (Day 1 through Day 7). The onset of individual SAR is defined as the time point after the injection at which the respective SAR first occurred.
- Summary of SAR with Grade 3 or higher
 - i. The number and percentage of participants who reported individual Grade 3 and/or higher solicited local AR and solicited systemic AR during the 7-day follow-up period after the injection will be tabulated by severity grade, and by severity grade and day of reporting.
- Summary of SAR Duration (SAR eDiary and SAR eCRF)
 - i. The duration of SAR in days will be calculated as the last date the SAR is reported - the first date the SAR is reported + 1.
- Summary of SAR Persisting Beyond 7 Days (SAR eDiary and SAR eCRF)

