PPSI will be used as the analysis population to summarize the immune responses (antibodies of interest) and the above summary statistics including GMT and GMFR will be provided by pre-booster/study baseline SARS-CoV-2 status.

The SRR is measured by an increase of SARS-CoV-2-specific bAb or nAb titer or value (level) from pre-booster below the lower limit of quantification (< LLOQ) to at least 4 x LLOQ, or a 4-fold or greater rise if pre-booster \geq LLOQ.

The SRR will be summarized at all measured time points for each treatment group with the 95% CI calculated using the Clopper-Pearson method. The difference of SRRs at all measured time points for mRNA-1273.529 compared with mRNA-1273 will be provided with 95% CI using Miettinen-Nurminen method. Analysis of the SRR will be performed in the PPSI-Neg. A sensitivity analysis of SRR will be performed in the PPSI by using stratified Miettinen-Nurminen method, with pre-booster positive, negative, and unknown SARS-CoV-2 status as strata.

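### Safety is a primary objective of a randomised comparison, yet no between-arm safety estimate is planned, so the size and precision of any excess over mRNA-1273 are never reported

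*Protocol*

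**What the plan says.** The protocol title announces "Immunogenicity and Safety of Omicron Variant Vaccines in Comparison with mRNA-1273 (Prototype) Booster Vaccine". The primary safety objective for Part 2 (SAP 2.1.2) is "To evaluate the safety and reactogenicity of mRNA-1273.214 and mRNA-1273 administered as a booster dose", and Part 1 has the parallel objective for mRNA-1273.529. Neither part has a safety hypothesis, margin or alpha.

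The planned intervals are these:

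- **Protocol synopsis and 9.6.3.** "A 2-sided 95% exact CI using the Clopper Pearson method will be provided for the percentage of participants with any solicited AR". Table 12 marks a 95% CI only in the row for any solicited AR (overall, local, systemic). Its note reads "95% CI using the Clopper-Pearson method, X = results will be provided". The other nine rows (unsolicited AEs, SAEs, AESIs, MAAEs, the three treatment-related categories, discontinuations and severe AEs) have a dash in that column.
- **SAP 6.3.2.** An exact Clopper-Pearson interval for the "percentage of participants who reported any solicited local AR, solicited systemic AR, or any SAR", and the same for reactions persisting beyond 7 days. Grade 3 or higher reactions are tabulated without an interval.
- **SAP 6.3.1.** "Analyses of unsolicited AEs will be summarized by stage, up to 28 days after vaccination and throughout the study and by treatment group". Only counts and percentages follow.

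No risk difference, risk ratio or other between-arm safety estimate appears in either document. For seroresponse, however, SAP 6.4.2.1.2 states that the between-arm difference "will be provided with 95% CI using Miettinen-Nurminen method".

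**The concern.** The concurrent randomised control arm allows the excess risk of the variant vaccine over the prototype to be estimated without confounding. The plan uses that contrast for titres (geometric mean ratios) and for seroresponse (rate differences), but not for safety, which is also primary. The report would therefore give no estimate of how many more recipients of the variant vaccine react, and no range of excess that the data can exclude. A reader wanting a comparison would be left to set two one-sample intervals side by side, which is a poor substitute for an interval on the difference. For unsolicited AEs, MAAEs, SAEs, AESIs and Grade 3 or higher reactions, there is not even a per-arm interval.

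**Working it through.** **Inputs from the documents.** Part 2 plans 1328 per arm in the fourth-dose group, and Part 1 plans 270 to 450 (protocol Tables 5 and 6). The SAP's treatment groups (6.1) separate third- and fourth-dose recipients, so these are the relevant denominators.

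**Assumed inputs.** The documents give no expected booster reaction rates. As illustrations I take rates that protocol 2.3.2 reports from the earlier mRNA-1273 trial: 65.3% (fatigue after dose 2), 23.9% (unsolicited AEs) and 1.1% (lymphadenopathy-related events). I add 5% and 80% to show the range for solicited categories.

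**The plan's own safety figure.** The sample size sections state at least a 90% chance of seeing one participant with an AE in each arm, at 1% incidence and 1328 per arm. Check: 1 − 0.99^1328 = 0.999998 in one arm, and 0.999997 in both. The statement is true with a wide margin (230 per arm gives 90% in one arm, 296 gives 90% in both). It concerns seeing an event within an arm and says nothing about an excess between arms.

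**Worked example, 1328 per arm.** Control 867 (65.3%), variant 920 (69.3%).

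- Clopper-Pearson 95% CIs: 62.7 to 67.8% and 66.7 to 71.8%. They overlap.
- Difference: 53/1328 = 4.0 points. Miettinen-Nurminen 95% CI: 0.4 to 7.6 points. It excludes 0.
- Hand check: SE = √[(0.6529 × 0.3471 + 0.6928 × 0.3072)/1328] = 0.0182, so 3.99 ± 1.96 × 1.82 gives 0.4 to 7.6.

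**Why the two readings differ.** Each per-arm half-width is about 2.56 points. The two intervals separate only when the difference exceeds the sum of the half-widths, 2.56 + 2.56 = 5.1 points. The interval for the difference excludes 0 when the difference exceeds about √(2.56² + 2.56²) = 3.6 points.

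**Range.** Smallest observed excess (percentage points) at which the difference CI excludes 0, and at which the two exact per-arm CIs stop overlapping:

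| Control rate | Per arm | Difference CI excludes 0 | Per-arm CIs separate |
|---|---|---|---|
| 5% | 1328 | 1.8 | 2.7 |
| 65.3% | 1328 | 3.6 | 5.1 |
| 80% | 1328 | 3.0 | 4.2 |
| 65.3% | 450 | 6.2 | 8.9 |
| 65.3% | 270 | 8.1 | 11.5 |

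The last column applies only where per-arm intervals are planned, that is, for solicited reactions. For the categories with no planned interval, a difference CI with 1328 per arm would exclude 0 from an excess of 3.4 points on 23.9%, or 1.0 point on 1.1%.

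**The case against.** Much can be said for the plan as written.

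- The safety objective is to evaluate, without a hypothesis, whereas the immunogenicity objectives are worded as comparisons. Per-arm description fits that objective.
- Counts and percentages are planned for both arms, so an excess is visible in the point estimates and anyone can compute a crude difference from the counts.
- Safety is to be judged by clinical review, with unblinded DSMB review during the study. Neither document makes overlap of per-arm intervals a decision rule.
- For rare SAEs and AESIs any interval for the difference will be wide. A difference CI that includes 0 can also be misread as showing no difference.

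All of this stands, and it limits the point. A reader might infer that a real excess of reactions could go unseen, or that the planned output would amount to a finding of no difference. The documents do not support either: the percentages are shown, and the misreading of overlapping intervals would be the reader's, not the plan's. Nor should the gap between the last two columns of the table be taken as power lost by a planned test, since there is none.

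The gap in estimation remains. A descriptive objective still calls for an estimate and its precision. DSMB review is monitoring, not a reported analysis. A difference computed from the pooled arm totals would not use the age stratification.

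**Conclusion.** The point holds as a gap in estimation and reporting. Neither document plans a between-arm estimate for any safety endpoint, and exact intervals are confined to any, local and systemic solicited reactions, including those persisting beyond 7 days. The size and precision of any excess over mRNA-1273 therefore go unreported. Anyone who falls back on comparing per-arm intervals could misjudge an observed excess of roughly 3.6 to 5.1 points in Part 2. In Part 1 the corresponding bands are 6.2 to 8.9 points with 450 per arm and 8.1 to 11.5 with 270. These figures assume a control rate of 65.3% and full fourth-dose enrolment; other rates move them as the table shows. No primary conclusion, error rate or stated safety rule is affected. It is a worthwhile and cheap improvement, not a flaw that invalidates the safety analysis.

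**What to change.** In protocol 9.6.3 and Table 12, and in SAP 6.3.1 and 6.3.2, add the risk difference (variant vaccine minus mRNA-1273) with a 95% Miettinen-Nurminen CI stratified by age group (16 to <65, ≥65 years), within the fourth-dose group of each part. Report it for:

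- any solicited local AR, any solicited systemic AR, and Grade 3 or higher solicited ARs;
- unsolicited TEAEs and MAAEs to Day 28;
- SAEs and AESIs.

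Label these estimates descriptive, with no hypothesis test and no multiplicity adjustment.

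Stratifying by dose number as well is not advisable. The Amendment 2 rationale says that only a few participants were randomised to a third dose, and the SAP reports the dose groups separately.

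The cost is a few table columns. The SAP already uses the Miettinen-Nurminen method, but its stratified version is by pre-booster SARS-CoV-2 status, with age group added only for BA.4/BA.5, so the strata would need to be respecified. The drawbacks are several intervals without multiplicity control, and wide intervals for rare events, though the width does show what the trial cannot exclude.
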